To assess the efficacy of custom-manufactured compression hosiery compared to off-the-rack compression hosiery for improving patient satisfaction and compliance with prescribed compression therapy.

- 1) Health-Related Quality of Life (HRQoL): We will use the short-form 12-item (SF12) HRQoL instrument for measuring HRQoL. It has been used widely and validated in many health conditions, and can be administered to patients in less than 5 minutes. It produces overall HRQoL estimates and subscale scores that assess both mental / emotional and physical functioning related to health.

2) Five-point satisfaction scale: This scale is used to assess the patient's pain management experience during their postoperative care. It consists of patients rating their overall postoperative pain management experience using a 5-point rating system. The scale ranges from 1 to 5, with 1 being "extremely dissatisfied", 2 "somewhat dissatisfied", 3 "Neutral/Neither satisfied nor dissatisfied", 4 "somewhat satisfied" and 5 "extremely satisfied" with their postoperative pain care. This rating has been used in other clinical trials and has been shown to be a reproducible assessment tool.

3) Brief Pain Inventory: The Brief Pain Inventory is a medical questionnaire used to measure pain, developed by the Pain Research Group of the WHO Collaborating Centre for Symptom Evaluation in Cancer Care.^{1,2}

Primary outcome measures

HRQoL, BPI and 5-point satisfaction scale will be assessed at baseline, at clinical follow-up at 90 days. Additionally, the BPI will also be administered via phone at 6 weeks.

Compliance with stocking use will be measured by a daily diary entry and will be the accumulated total of hours worn over 90 days.

H. SECONDARY OBJECTIVES

- To identify subgroups that may benefit more from custom hosiery.
- To determine whether improved fit affects likelihood to progress to invasive treatment.

Secondary outcome measures

- The sample size (200 subjects) will allow us to investigate subgroup effects. Preliminary a priori hypotheses are that patients with difficult to fit legs (eg., large calf/ankle ratio) will have significant improvements in compliance and satisfaction with custom fit hosiery.
- Progression to ablation therapy will be determined by patient preference for further intervention. We will measure efficacy as a simple proportion between the randomized groups.

IX. STUDY POPULATION

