The target population of our study will be comprised of patients that are 18 years-old and above that present to our group at The University of Texas Medical School at Houston with venous disease requiring treatment with compression.

Inclusion/Exclusion Criteria

Patients will be *eligible for the study if:*

- 18 years-old or older, and
- Ability to comprehend and sign an informed consent and complete study questionnaires
- Patient is participating in usual work and home activities with no changes anticipated for the duration of the study
- The use of compression stocking is prescribed in accordance with the usual practice and management of venous disorders
- The patient will confirm they are willing to pay for the compression stockings.

Patients will be *excluded from the study if:*

- The patient has a known allergy to any component of the stocking (latex, etc)
- The patient has non-venous source of pain in either leg that could, in the opinion of the investigator, confound the results of the study i.e. Neuropathy, Arterial insufficiency, Diabetes
- The patient is confined to bed
- The patient has uncontrolled Congestive Heart Failure
- The patient has acute dermatitis
- The patient has weeping dermatosis
- Patients with venous ulcers will be excluded.

Protocol Deviation:

- Patient is randomized but does not receive the correct treatment assignment

Withdrawal criteria:

- Voluntary: patients who had consented and enrolled in the trial will maintain their right to withdraw at any point during the study as explained in the informed consent.
- In case of unexpected/unpredicted events, the Principal Investigator and research staff may determine that patient meets criteria for withdrawal.

X. STUDY DEVICES

The Custom stocking, (Isobar Compression Garment) is an FDA Class 1 device. The control stocking (Sigvaris) is also an FDA Class 1 device. These devices are rated at 15 mmHg compression and are comparably priced.

XI. STUDY SCHEDULE

Expected start date after IRB Approval: Eligible to begin January 2017

Expected end date for enrollment: January 2019

Length of treatment-phase enrollment for each patient: 90 days

Length of follow-up for each patient: 90 days from initiation of compression for primary endpoint; six months for assessment of likelihood to receive follow-on ablation therapy.

XII. STUDY DESIGN/METHODOLOGY

This will be a single institution, prospective, blinded, randomized, controlled

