clinical trial with a 2-arm parallel-group design to assess the efficacy of custom-fitted compression hosiery vs off-the-rack compression hosiery.

The custom stockings take 2 weeks to manufacture. In order to maintain the blind, stockings will be procured by the UT CV Surgery purchasing personnel and distributed to the subjects in unmarked packaging within three weeks of randomization. Neither the prescribing physician nor the patient will know the treatment assignment.

Screened patients meeting the eligibility criteria will have a below-knee laser measurement scan, and will be randomized into one of the two study groups.

At the screening visit, patients will be evaluated for trial eligibility and the study will be explained. For eligible patients who wish to participate, informed consent will be obtained and the patient will receive history and physical exam and will complete baseline HRQoL and pain scale surveys. Volumetric scans will be performed and the data will be stored. Patients will be randomized by a study coordinator, and will be instructed to expect stockings in the mail within 3 weeks.

After stockings are dispensed, patient should call the office to inform the study nurse or coordinator of the day they are beginning therapy, and biweekly log will be kept as a measure of compliance.

Patients in the study should also complete the Brief Pain Inventory (BPI) before randomization (at baseline following enrollment), by phone during week six, and at clinical follow-up after completing 90 days of compression therapy. Additionally, patients will be assessed on their satisfaction at week six and at 90-day clinical follow-up. This

will be done using the 5-point satisfaction scale with 1 being “very dissatisfied” to 5 being “very satisfied”. The SF-12 HRQoL instrument will also be completed at enrollment, at six weeks and at 90-day follow-up. This will conclude the 90-day treatment period. Patients will be re-contacted at six months post-treatment to determine whether they are still using their stockings (or have replaced them) or have progressed to invasive treatment. After the six-month assessment, the study will be concluded and enrollment will be terminated.

Study Conduct

1. Screening

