
Randomization and allocation concealment will be performed by study personnel using a restricted-access randomization file. The sequence will be generated by a UT

statistician in a random permuted block design and copied to a secure drive accessible only to unblinded study personnel. At enrollment patients will be assigned a study ID number. The laser scan data will be identified by this study number and noted in the CRF. Depending on the group assignment, either an order for a custom pair of stockings will be generated and tagged to the scan data – which will then be transmitted to the manufacturer – or the appropriate pair of Sigvaris stockings will be procured. After two weeks, the stockings as allocated by randomization will be packed in unbranded packaging and mailed to the research subject by trackable means (UPS, FedEx, US Postal Service, etc.). The clinical personnel who assess the patients will not handle the hosiery and will not see it on the patient. The patient will not know whether the stockings are custom or off-the-rack, so the double masking will be maintained.

5. Baseline assessment

History, physical exam and review of symptoms will be conducted at enrollment and captured to an electronic case report form that will be implemented at UT in REDCap. The examining physician will draw a diagram of the involved veins for comparison with the 90-day examination. Pain assessment and HRQoL will be captured as described previously.

6. Follow-up

After the initiation visit is completed, the follow-up will be:

- i. Compression therapy per physician directive throughout 90 days with a compliance log to be kept bi weekly.*

- ii. *At 6 weeks questionnaire completion via phone.*
- iii. *At 90 days clinic follow-up and questionnaire completion*
- iv. *At six months after treatment initiation by telephone*

7. Termination of enrollment

Patient will be considered to have his/her enrollment terminated:

- i. *After completion of the six month telephone survey*
- ii. *If any medical/surgical/environmental condition develops that would affect or impair primary or secondary outcomes measurements results*
- iii. *If the study is terminated*
- iv. *If the patient dies*

8. Termination of Study

- i. *End of study period*
- ii. *Unanticipated safety problems that would make continuation unethical*
- iii. *If the trial does not look as though it can achieve its enrollment targets within two years*

XIII. ADVERSE EVENT REPORTING

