Patients enrolled in the trial will be instructed to report any unwanted effect at any time during the study. For this study, only adverse events that are directly related to the use of compression stocking will be reported. Expected adverse effects of compression therapy will be described to the patients during the screening/enrollment as well as in the informed consent process. Most adverse side effects are minor and may include rash, contact dermatitis, discomfort, lack of symptomatic relief, and in rare cases, local skin ischemia and breakdown.

Safety monitoring will include assessment of:

- i. Adverse Effects (AE)
- ii. Vital Signs
- iii. Wound healing status
- iv. Pain
- v. Satisfaction

All parameters will be closely monitored in a continuous manner, as part of our standard clinical care. Any abnormalities found will be promptly assessed and described in the patient's medical records. Patients will be instructed to call the clinic if problems arise, and will also be assessed at clinic visits. If need be, an immediate unscheduled visit shall be arranged if the patient so desires.

The PI will review AEs as they occur, and requirement for changes to the study design or device use will be determined on an ongoing basis. This study does not require a DSMB.

XIV. STATISTICAL ANALYSIS PLAN

A. Primary Outcomes

The trajectory of BPI, HRQoL and Patient Satisfaction scores at 45 and 90 days of treatment will be measured by mixed-effects linear models between the groups.

Appropriate score transformations will be performed as necessary to meet distributional assumptions of the tests. Randomization is expected to balance the groups with respect to pre-intervention risk factors.

Total time worn over 90 days as reflected in diary entries will be compared by Wilcoxon rank-sum test between the two groups..

A. Secondary Outcomes

[figure not shown]
Additional analyses will be performed to determine whether patient characteristics such as calf/ankle ratio and other measurements made using laser scan data show differential (interaction) effects in the custom-stocking group vs the off-the-rack group.

Progression to ablation will be measured as simple test of proportions (Fisher's Exact test) of those seeking ablative therapy in the custom vs OTR groups.

B. Sample Size Determination

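### The 90-day window runs from patient-reported start of compression, so never-starters have no defined outcome window and a delayed start is not counted as non-compliance

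*Combined protocol and SAP*

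**What the plan says.** Section VII makes compliance a primary outcome. It is recorded in a daily diary and "will be the accumulated total of hours worn over 90 days". Section XII describes the recording differently: a "biweekly log will be kept as a measure of compliance".

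Section XI (Study Schedule) sets follow-up at "90 days from initiation of compression for primary endpoint". Under section XII (Study Design/Methodology), stockings are "distributed to the subjects in unmarked packaging within three weeks of randomization", after which the "patient should call the office to inform the study nurse or coordinator of the day they are beginning therapy". The final BPI is taken "at clinical follow-up after completing 90 days of compression therapy". Section XII, item 6 (Follow-up), instead starts follow-up after an initiation visit that is defined nowhere, although the stockings arrive by post. Item 4 has them "mailed to the research subject by trackable means (UPS, FedEx, US Postal Service, etc".

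Section XIV gives the analysis: "Total time worn over 90 days as reflected in diary entries will be compared by Wilcoxon rank-sum test between the two groups". It names no analysis set. It gives no rule for a patient who never starts, who reports no start date, or who has no diary.

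**The concern.** The time origin of the primary endpoint is set after randomization, by the patient. Someone who tries the stocking, finds it uncomfortable and puts it away may never start. Fit is the property under test, so starting may depend on the arm. Never starting is also the extreme of non-compliance, and compliance is a primary outcome.

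Two consequences follow. First, a never-starter has no day 0 from which to count week six or day 90, and no reason to keep a diary. A rank test on diary totals has no value for that patient unless a rule supplies one. Second, a patient who waits before starting gets the same 90 days as everyone else, so the days of non-use after delivery do not reduce the total. If either behavior differs between arms, part of the treatment effect on compliance goes unmeasured. The satisfaction, BPI and SF-12 follow-up scores of never-starters may be lost as well.

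**Working it through.** The documents contain no compliance figure to reproduce. The sample-size text in section XIV concerns the proportion with HRQoL improvement, and only its 100 patients per arm is used here. Hours, standard deviations, never-start rates and the 5% test level are assumptions.

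1. **Three patients traced through the text.** One who starts on delivery has a 90-day window and a diary total. One who starts 14 days later has a 90-day window that opens 14 days later. One who never starts has no initiation date, no six-week or 90-day date that can be counted from it, and no diary total.

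2. **Late start.** Assume 600 h in 90 days, that is 600/90 = 6.67 h/day. Counted from initiation, any starter scores 90 × 6.67 = 600 h. Counted over 90 days from delivery, a 14-day delay gives 76 × 6.67 = 507 h and a 30-day delay gives 60 × 6.67 = 400 h. The plan's anchor therefore hides 93 h and 200 h of non-use.

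3. **Never-starters: what each rule estimates.** Let q be the never-start proportion and μ the mean hours among starters (C custom, O off-the-rack). If never-starters are dropped, the mean difference is μ_C − μ_O. If they are scored zero, it is (1 − q_C)μ_C − (1 − q_O)μ_O.
   - Equal wear of 600 h, 5% C and 15% O: dropped 0 h; zero 0.95 × 600 − 0.85 × 600 = 60 h. Expected never-starters: 5 + 15 = 20 of 200.
   - Equal wear, 5% and 10%: zero-scored difference 30 h. With 5% and 20%: 90 h.
   - 8 h/day off-the-rack (720 h) and 8.7 h/day custom (783 h), 5% and 15%: dropped 63 h; zero 0.95 × 783 − 0.85 × 720 = 132 h.

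4. **Effect on the Wilcoxon test.** Simulation with 100 per arm. Set A: starters' hours roughly Normal, mean 600 h, SD 200 h, 4,000 runs. Set B: mean 8 h/day, SD 2.5 h/day, 3,000 runs. Where repeat runs of set B differed, the range is shown.

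| Set | Never start, custom / off-the-rack | True difference among starters | Significant if dropped | Significant if scored zero |
|---|---|---|---|---|
| A | 5% / 10% | none | 5% | 9% |
| A | 5% / 15% | none | 5% | 23% |
| A | 5% / 20% | none | 5% | 45% |
| B | 5% / 15% | none | 5% | 23–24% |
| B | 5% / 15% | 0.7 h/day | 43–46% | 79–81% |
| B | 5% / 10% | 0.7 h/day | 46% | 62–63% |
| B | 5% / 5% | 0.7 h/day | 47% | 41% |
| B | 10% / 10% | 0.7 h/day | 43–44% | 32–34% |
| A | 10% / 10% | 60 h | 49% | 38% |
| B | 10% / 5% | 0.7 h/day | 46% | 19% |

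With more never-starters off-the-rack, dropping them hides a real compliance difference. With equal rates, zero-scoring adds tied low values in both arms and costs power. With more never-starters in the custom arm, the two rules diverge the other way.

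**The case against.** The strongest reply is that this is a gap in wording and that hours from initiation are a legitimate on-treatment measure. Four stronger readings are tempting, and the documents do not support them.

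- **Late starters have no window.** They do. Section XI gives each of them 90 days from initiation; only their delay goes uncounted.
- **The phone call starts the clock.** The anchor is initiation, and the call reports it. Someone who starts without calling has still initiated and can keep a diary.
- **The plan excludes never-starters.** It does not say so. Zero hours is also compatible with the text, and the six-week and 90-day contacts are not expressly conditional on the call. Removal from the BPI and SF-12 analyses is likewise an inference: baseline scores are collected, and the plan does not say whether the mixed models keep baseline-only patients.
- **The bias must run toward no difference, and zero-scoring always helps.** Both depend on more never-starting off-the-rack, for which the documents give no rates. Patients must be willing to pay for the stockings, and the protocol says compression is required before ablation is preauthorized, so never-starting may be uncommon.

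The reply also notes correctly that timing assessments from delivery means late starters are scored after less exposure. What remains is that the stated time origin is post-randomization and open to influence by fit, and that a test on diary entries omits patients without diaries unless a rule is written. Choosing between dropping and zero after the data are seen could change a primary result.

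**Conclusion.** The concern holds in this limited form. The primary window is anchored to patient-reported initiation, never-starters have no defined window or analysis rule, and delay in starting is not counted as non-compliance. Omission of never-starters is the likely default, not a written rule.

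The size is conditional. At 5% custom and 15% off-the-rack never starting, with equal wear among starters, the choice of rule moves the chance of a significant result from about 5% to about 23%. At 5% and 10% it moves only to about 9%. At 10% in both arms with a true 0.7 h/day difference, zero-scoring lowers power from about 44% to about 33%. These rates and hours are illustrations; nothing in the documents fixes them. The case for change is therefore that the compliance comparison should cover everyone randomized under a rule set in advance, whatever that does to power. It should be settled before analysis.

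**What to change.** For the compliance outcome:

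- Set day 0 for every randomized patient at the tracked delivery date, recorded in the case report form. That date precedes the decision to start.
- Analyze all randomized patients over 90 days from that date. Count pre-start days and confirmed never-starters as zero hours.
- Keep missing diaries from patients who did start separate from true zeros, with their own prespecified handling.
- Report time from delivery to start descriptively, and keep total hours from initiation as a supportive analysis.

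For the other outcomes, make the planned week-six call and day-90 contact for all randomized patients, whether or not therapy was started or completed. Reconcile section XI, the main text of section XII and its item 6 on when follow-up begins, and define or remove the initiation visit.

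The cost is mainly protocol and SAP wording, since tracked mailing and the six-week call are already planned. There are three downsides. Mean hours worn will look lower. Power falls if never-start rates are similar in the two arms. Late starters' BPI, satisfaction and SF-12 scores will reflect slightly less exposure than under the present anchor.

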The PI and research staff will assess patients as possible candidates for enrollment based on the inclusion criteria described previously. A member of the research team - the PI, a Co-investigator, research coordinator, or research nurse will obtain the consent from interested patients who met the preliminary inclusion criteria. The consent process will take place during the clinic visit. Patients will be given adequate time and education about their condition to ask questions about the protocol and research study. Those who wish to participate will be informed they are responsible for the cost of the hosiery as it may not be covered by insurance (most plans do not cover stockings even though they are required prior to preauthorization for ablation therapy). Patients would be responsible for this cost whether or not they are enrolled in the trial – no additional cost to the patient will result from trial participation. The preoperative baseline pain level, using BPI and HRQoL will be recorded at this time. A copy of the signed informed consent shall be provided to the patient, a copy will be

placed in the patient's hospital chart, and a copy will be kept by the research team. Medical/surgical history, vital signs measurements, and standard clinical testing will also be performed as per the usual practice for assessment and management of CEAP class 2-5 venous disease.

2. Quality of life assessment - Brief Pain Inventory

The impact of pain on patient's quality of life will be assessed through a brief pain inventory (BPI) that should be done at enrollment, at the six week point during compression therapy and at the final clinic visit after 90 days of treatment. The BPI will be presented as an easy to comprehend questionnaire for the patients to quantify and communicate their pain experience and how it is affecting their life. It is designed such that patients with 6th-grade education should be able to complete the questionnaire on their own. Question and answers will be provided in a check-box format. The BPI that will be used on this study will be the short version. Patients with difficulty reading or who are physically unable to complete the questionnaire will be assisted by the research team based on their verbal responses to the BPI questions.

3. Enrollment

After screening for eligibility, if all inclusion/exclusion criteria are met and the patient has consented; the patient will be enrolled in the trial.

4. Randomization and Allocation Concealment

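### The BPI, a primary outcome, is not tied to leg pain, so pain elsewhere that was present at entry may dilute the comparison; one fixed instruction would prevent this cheaply

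*Combined protocol and SAP*

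**What the plan says.** The BPI is listed among the primary outcome measures (protocol Section VII): "HRQoL, BPI and 5-point satisfaction scale will be assessed at baseline, at clinical follow-up at 90 days". A further BPI is taken by phone at six weeks. The analysis plan (Section XIV.A, Primary Outcomes) treats it accordingly: "The trajectory of BPI, HRQoL and Patient Satisfaction scores at 45 and 90 days of treatment will be measured by mixed-effects linear models". That section names no BPI item or subscale and no pain site, and does not say whether baseline BPI enters the model.

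The instrument is described in general terms. Section VII, item 3: "The Brief Pain Inventory is a medical questionnaire used to measure pain". Section XII, Study Conduct, item 2 says patients will use it to "quantify and communicate their pain experience and how it is affecting their life", and adds: "The BPI that will be used on this study will be the short version". Neither place tells the patient which pain to rate.

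Two provisions deal with pain or other conditions that could disturb the outcomes. Section IX excludes a patient if: "The patient has non-venous source of pain in either leg that could, in the opinion of the investigator, confound the results of the study". Section XII, Study Conduct, item 7 (ii) ends a patient's enrollment: "If any medical/surgical/environmental condition develops that would affect or impair primary or secondary outcomes measurements results".

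**The concern.** The exclusion in Section IX shows that the authors saw non-venous pain as a threat to the results, but it closes only part of the gap. It is limited to the legs and rests on the investigator's opinion. Long-standing back, neck or shoulder pain does not bar entry, yet it can enter a score with no stated site.

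The treatment acts on the lower leg: Section XII describes a below-knee scan, from which a below-knee garment is inferred. Pain that stockings cannot change either replaces the leg pain in a patient's answer, which shrinks the average difference between arms, or adds to it, which increases the variance. With no fixed referent, the same patient might also rate different pains in clinic and by phone.

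At stake is the power of one primary outcome and the reading of a null BPI result, which would leave open whether custom stockings fail to help leg pain or whether the question asked about other pain as well.

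**Working it through.** **Comparing the sections.**

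| Question | Where | Answer |
|---|---|---|
| Is the BPI primary? | VII; XIV.A | Yes |
| Is a pain site given to the patient? | VII item 3; XII Study Conduct item 2 | None stated |
| Is non-leg pain present at entry excluded? | IX | No; legs only, discretionary |
| Is new interfering pain handled? | XII Study Conduct item 7 (ii) | Partly; only conditions that develop after entry |
| Is other pain recorded or adjusted for? | XIV.A | Not stated |
| Is it balanced between arms? | XIV.A | Left to randomization |

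A patient with stable shoulder pain at enrollment meets none of the listed exclusions by reason of that pain, is not reached by the termination rule, and is given no stated reason to leave that pain out of the BPI.

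**Illustration of size.** The plan has no BPI power figure to reproduce. Its sample-size section concerns the proportion of patients with improved HRQoL. Only the 100 per arm is taken from it.

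Assumptions, none from the documents:
- two-sided 5% test;
- a true effect on leg pain of 0.40 SD, chosen because it gives 80% power at this size: (1.960 + 0.842) × √(2/100) = 0.396;
- a two-sample t-test at one time point, as a simple stand-in for the mixed model.

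*Model 1: a share q of patients rate only pain that stockings do not change.* Effect = 0.40 × (1 − q). Required n per arm = 100 / (1 − q)², rounded up.

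| q | Effect (SD) | Power at 100 per arm | n per arm for 80% |
|---|---|---|---|
| 0 | 0.40 | 80.4% | 100 |
| 10% | 0.36 | 71.7% | 124 |
| 20% | 0.32 | 61.5% | 157 |
| 30% | 0.28 | 50.4% | 205 |

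*Model 2: other pain only adds noise, making up a share v of the total variance.* The total SD is 1/√(1 − v), so the standardised effect = 0.40 × √(1 − v).

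| v | Effect (SD) | Power at 100 per arm |
|---|---|---|
| 10% | 0.379 | 76.1% |
| 20% | 0.358 | 71.1% |
| 30% | 0.335 | 65.4% |

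A normal approximation starting from 0.396 SD gives almost the same values: 71.3%, 61.1% and 50.1% for Model 1, and 75.7%, 70.7% and 65.0% for Model 2.

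**The case against.** **The form and phone script are not in the documents.** Either may already direct the patient to the leg. This stands: the documents show only that the protocol states no pain site. They do not show that patients will score other pain.

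**A general measure may be intended.** Study Conduct item 2 is headed as a quality-of-life assessment, the objectives do not name venous leg pain, and the SF-12 is generic too. This has some force, but the leg-pain exclusion shows that non-venous pain was regarded as contaminating the result, and the SF-12 already supplies a generic measure.

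**New pain is not simply counted.** A reader might infer that any non-leg pain arising during the 90 days enters the BPI. Study Conduct item 7 (ii) does not support so absolute a reading, since enrollment can end when an interfering condition develops. It does not reach pain present at entry.

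**There is no bias between arms.** A reader might infer that other pain distorts the comparison in favour of one arm. Randomization should balance it, so the loss is of sensitivity only.

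**The power figures are hypothetical.** The effect and the shares are assumed, and Model 1 is the harsher model because it gives affected patients no response at all. Repeated measures with a baseline could absorb part of any stable other pain, although the plan does not say how baseline is used. The requirement that patients be in their usual work and home activities also makes severe or changing pain elsewhere less likely, and hip pain might be judged leg pain. All of this stands and limits what can be said about size.

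**Conclusion.** The point holds as a cheap improvement to a primary outcome. As written, the protocol admits patients with existing pain outside the legs and does not tell them to leave it out of the BPI. This can dilute the between-arm difference or add noise to it, and would make a null BPI result harder to interpret.

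The real size cannot be derived from the documents. Under the stated assumptions, with 10% to 30% contamination, power drops from 80% to between about 72% and 50% if other pain replaces leg pain, and to between about 76% and 65% if it only adds variance. These figures show that modest contamination could matter; they do not estimate this trial's power. The conclusion also assumes that no leg instruction stands on the unseen form or script. If one does, the remaining task is to state it in the protocol.

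**What to change.** - **Sections VII (item 3) and XII (Study Conduct, item 2):** add one fixed instruction to the BPI at baseline, in the week-six phone script and at day 90, for example: *Answer all questions about pain in the leg(s) for which you were prescribed stockings.* Staff who help a patient complete the form should read out the same sentence.
- **Section XIV.A:** name the leg-referred BPI score that is the outcome (severity, interference, or both) and state that baseline BPI enters the mixed model. The instruction alone would leave the outcome undefined, because no BPI score is named at present.

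This needs no extra patients or visits. The cost is one line on the form and script and a short addition to the analysis plan. The downside is a small departure from the standard questionnaire wording, identical in both arms and at all visits.
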